**Northern Health and Social Care Trust (NHSCT)**

**Screening** Members of the direct care team will screen their patient lists for potentially eligible participants.

**Invitation** The first communication about the pilot will be from the direct care team at the hospital or via a poster advertising the SHAPES pilot that will be displayed on information boards located within NHSCT Hospitals and on official NHSCT, MEAAP and MOIC social media feeds. The poster will direct potential participants interested in the pilot to contact the research team directly. Alternatively, the direct care team may invite potentially eligible participants to participate in-person at a clinic/hospital attendance, over the phone or via a written invitation (electronic or paper).

**Information sheets** Information sheets will be provided to potentially eligible participants in-person or via post or email either by the direct care team or the research team (if contacted directly or consent to contact is documented). A minimum of 24 hours will be provided to allow time to consider the information provided before consent is obtained.

**Consent to contact** Verbal consent to be contacted may be provided by potential participants to their direct care team to allow the provision of contact name and telephone number of the potential participant to the research team. This will be documented by the direct care team. The research team may then attempt to contact the potential participant by phone.

**Eligibility confirmation** Eligibility may be confirmed by the direct care team. The research team may also confirm eligibility if potential participants make direct contact with them or if participants have provided consent to contact. Eligibility may be confirmed either in-person or over the phone and documented.

**Consent** Eligible participants will be required to provide written consent. The direct care team may obtain consent. The research team may obtain consent if contacted directly by the potential participant or if verbal consent to contact has been received. Voluntary, informed consent for all participants may be obtained in-person or remotely with the following format of signatures collected where appropriate:

- Handwritten
- Typewritten
- Scanned
- An electronic representation of a handwritten signature
- Handwritten signature posted to research personnel

## **Mid and East Antrim Agewell Partnership (MEAAP)**

**Screening** MEAAP project officers will screen their client lists for potentially eligible participants. Potentially eligible participants may be contacted in-person, over the phone or via a written invitation (electronic or paper).

**Invitation** The first communication about the pilot will be from a project officer from MEAAP. This may occur in-person, over the phone or a written invitation (electronic or paper).

**Information sheets** If potential participants are interested in the pilot their MEAAP project officer or member of the research team (if consent to contact obtained) will provide further information about the pilot. A minimum of 24 hours will be provided to allow time to consider the information provided before consent is obtained.

**Consent to contact** Verbal consent to be contacted may be provided by potential participants to their MEAAP project officer to allow the provision of contact name and telephone number of the potential participant to the NHSC research team. This will be documented by the project officer. The research team may then attempt to contact the potential participant by phone.

**Eligibility confirmation** Eligibility may be confirmed by the MEAAP project officer. The research team may also confirm eligibility if potential participants make direct contact with them or if they have provided consent to contact. Eligibility may be confirmed either in-person or over the phone and documented.

**Consent** Eligible participants will be required to provide written consent. The project officer may obtain consent. The research team may obtain consent if contacted directly by the potential participant or if verbal consent to contact has been received. Voluntary, informed consent for all participants may be obtained in-person or remotely with the following format of signatures collected where appropriate:

- Handwritten
- Simple electronic signature (e.g. tickbox and declaration, typed name and date) Scanned
- An electronic representation of a handwritten signature
- Handwritten signature posted to research personnel

### *Withdrawal of consent*

Participants can withdraw from the study at any point, no reason needs to be provided, however, the participant will be asked if they would like to state a reason for withdrawal.

Clarification will be sought as to whether the participant would like to withdraw all data or if data provided up to the point of withdrawal may be retained and used in the analysis and description of the pilot cohort.

The following details will be noted upon withdrawal of consent; date, reason (if provided), whether consent for a follow-up interview or consent to use data until date of withdrawal remains.

### *HSC staff recruitment*

A list of appropriate professionals will be identified from the research team's knowledge and contacts. An invitation email containing information about SHAPES and a request to conduct an interview and demonstrate the intervention will be sent. If the request is accepted an information sheet will be provided and the research team will obtain consent. Voluntary, informed consent for all participants may be obtained in-person or remotely with the following format of signatures collected where appropriate:

- Handwritten
- Simple electronic signature (e.g. tickbox and declaration, typed name and date) Scanned
- An electronic representation of a handwritten signature
- Handwritten signature posted to research personnel

### 3.8 Data collection, management and analysis

#### 3.8.1 Service user data collection methods

The majority of data collection will be conducted remotely. The exception to this is the face-to-face, one-to-one introduction to the app and devices. This will be conducted in person if the current local COVID-19 situation permits and this is the participant's preference. The procedures below may be completed in person or remotely depending on the current COVID guidelines and participant preference.

##### *Service user prior to baseline procedures*

- Screening
- Eligibility confirmation
- Informed consent
- Training on use of SHAPES app and connected devices
- Run-in, familiarisation with devices
- Contact details — name, address, email, phone number, alternative contact name and phone number, Health and Care number

##### *Service user baseline procedures*

- Questionnaires — Barthel Index, Gijon Scale, EHFS, MARS, BMQ, EQ-5D-5L, GSES, OSSS-3, HLM1, participation measure, WHOQOL-BREF
- Medical history data — height, weight, left ventricular ejection fraction, heart rhythm, implanted devices, medical conditions, heart failure stage, dyspnoea level, smoking status, leg pain symptom question
- Demographic data — including DOB, education, sex, marital status, occupational status, caregiver status, housing details
- Technical data — device monitoring details e.g. model, manufacturer, serial number and preferred time of day for reminders/questionnaires, make and model of the participants own smartphone/tablet
- Laboratory results — urea, creatinine, sodium, potassium, haemoglobin, cholesterol, eGFR, HbA1c, ACR, urine creatinine, urinary albumin-creatinine ratio
- Unscheduled care — hospitalisations (previous 3 months), and previous month hospital readmissions, A&E attendances, out of hours care, specialist service contacts, emergency ambulance call outs

- Current prescribed medication — name, frequency, strength, chronic or as required, stop date if stopped during the pilot, start date if started during the pilot.

*Service user study visits and procedures*

- During the pilot, the participant will be asked to record the following at least once daily, as appropriate, via the SHAPES app; blood pressure, heart rate, oxygen saturation, weight (which will include body mass index, body fat, visceral fat, skeletal muscle, basal metabolic rate).
- Participants diagnosed with diabetes and monitoring blood glucose regularly will be requested to record their blood glucose with the same frequency as directed by their doctor on the SHAPES app.
- Participants diagnosed with heart failure will be asked a series of daily questions about their heart failure symptoms administered via the SHAPES app.
- All participants will be asked about their adherence to medication with a weekly MARS questionnaire administered via the SHAPES app.
- During the pilot, the patient may view their medication list
- Unscheduled care updates — any updates to baseline hospitalisations, hospital readmissions, A&E attendances, out of hours care, specialist service contacts, emergency ambulance call outs recorded from medical notes
- Prescribed medication updates — any updates to prescribed medications notified by participant
- Tracking data — log data on how the participant uses the SHAPES app e.g., date/time of usage, what functionalities were accessed
- Adverse events — date, start time, injury description, incident description, action taken, location of incident (private home or healthcare facility)
- Researchers will document any contact received/provided regarding support required to facilitate the pilot (date, duration, reason)

*Service user end of pilot visit (+14 days)*

- Questionnaires — UEQ-S, SUS, MARS, BMQ, EQ-5D-5L, GSES, OSSS-3, HLM1, participation measure, WHOQOL-BREF, technology acceptance measure
- Participant may participate in an interview at this time or a separate date may be accommodated.
- Demographic data — marital status, occupational status, caregiver status, housing details

*Service user follow-up study visits and procedures*

- If an interview is to be conducted this may occur at a mutually convenient time after the intervention has been completed.
- 3 month follow-up data collection (+/- 7days):
- Questionnaires — EQ-5D-5L, GSES, OSSS-3, HLM1, participation measure, WHOQOL-BREF

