Participants will receive one-on-one, face-to-face introduction to the app and training on how to use both it and the connected medical devices. A user manual will contain detailed step-by-step supportive guidance and information, and will be provided to participants in hard-copy format for reference by participants during the pilot. There will be a run-in period of approximately one week wherein the participant can familiarise themselves with the app and liaise with the researchers to troubleshoot any problems they may be experiencing with the technology. Participants will be asked to use the app and connected devices for 12 weeks. Researchers will contact participants by telephone at the end of week 1, if there are three or more consecutive days where no data has been received (up to a maximum of four times during the pilot) and monthly (if required) thereafter. These telephone contacts are to enable the researchers to support participants with their use of the technology and troubleshoot any issues they may be experiencing (no health advice or clinical support will be provided by the researchers. If participants have any health concerns they will be encouraged to contact their specialist care team).

All data entered or transferred into the SHAPES app (i.e., clinical readings, survey responses) is pseudonymised and will be stored in the technical partners' (EDGE and GNOMON) servers and then uploaded to the SHAPES big data platform. Selected data is then processed by two further SHAPES digital solutions; a heart failure decompensation risk prediction algorithm (VICOM) and an analytic tool that generates personalised dynamic thresholds for participants' clinical parameters (TREE). These digital solutions have not yet been validated or CE-marked for use as medical devices. Therefore, the outputs will not be used to inform clinical care, but rather to determine whether the digital solutions are capable of producing outputs reliably using the available data, and to indicate if there are any associations between the risk scores generated and the participants' use of unscheduled care.

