#### *Secondary outcomes*

- Participants' user experience with the SHAPES app as measured using the User Experience Questionnaire –short version (UEQ-S)
- Usability of the SHAPES app as measured using the System Usability Scale
- Number and rate of successful registrations of each clinical parameter per participant, per day (heart rate, blood pressure, weight, oxygen saturation, blood glucose)
- Number and rate of control limits (upper and lower) successfully generated by the 'Vitals Control' analytic tool per person (rate defined as number of pairs of limits generated per week during the pilot)

- Number and rate of heart failure decompensation prediction (HFPred) risk scores successfully generated per person (rate defined as number of scores generated per week during the pilot)
- Change in hospitalisation rate per person (hospitalisations/month) and A&E attendance rate (attendance/month) three months prior to baseline compared with 3 months during the pilot
- Participants' self-reported medication adherence as measured using the Medication Adherence Report Scale (MARS) at baseline and at the end of the pilot
- Participants' beliefs about medicines as measured using the Beliefs about Medicines Questionnaire (BMQ) at baseline and at the end of the pilot
- Correlation between participants' self-reported medication adherence and beliefs about medicines
- Number and rate (score/week) of heart failure decompensation prediction (HFPred) risk scores successfully generated per person during the pilot
- Correlation between HFPred scores and unscheduled care during the pilot (unscheduled care defined as composite of hospitalisations, A&E attendances, specialist contacts, out-of-hours contacts)
- Health-related quality of life as measured using the EQ-5D-5L questionnaire (ref) at baseline and at the end of the pilot
- Exploration of healthcare practitioners' views on integration and alignment of the SHAPES platform and Digital Solutions with current care pathways
- Exploration of healthcare practitioners' views about their trust and acceptance of the SHAPES platform and Digital Solutions
- Exploration of participants' views about their trust and acceptance of the SHAPES app.
- Exploration of user engagement behaviors

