| To validate the capability of the SHAPES platform and Digital Solutions to implement a personalised approach to achieve safe and effective use of medicines in homes.                         | Number and rate of successful registrations of each clinical parameter per participant, per day (heart rate, blood pressure, weight, oxygen saturation, blood glucose)                                      | End of pilot   |
|  | Number and rate of control limits (upper and lower) successfully generated by the 'Vitals Control' analytic tool per person (rate defined as number of pairs of limits generated per week during the pilot) | End of pilot   |
|  | Number and rate of heart failure decompensation prediction (HFPred) risk scores successfully generated per person (rate defined as number of scores generated per week during the pilot)                    | End of pilot   |
|  | Number and rate of views of medication list (rate as defined as number of views per week during the pilot)  | End of pilot   |
| To validate the capability of the SHAPES platform and Digital Solutions to achieve better patient outcomes by initiating, developing and sharing best practice with regards to medicines use. | Change in use of unscheduled care related to heart failure and diabetes as measured by: 
 
• Rate of hospitalisation
 
• Rate of A&E attendance
 
   | 3 months prior to baseline and end of pilot
3 months prior to baseline and end of pilot |

|  |   |                           |
|--|---|---------------------------|
| To validate the capability of the SHAPES platform and Digital Solutions to address and improve deficiencies with adherence to medicines and treatments.                            | Medication Adherence Report Scale (MARS)  | Baseline and end of pilot |
|  | Beliefs about Medicine Questionnaire (BMQ)  | Baseline and end of pilot |
|  | Correlation between participants' self-reported medication adherence and beliefs about medicines  | After pilot               |
| To validate the capability of the SHAPES platform and Digital Solutions to improve data collection to develop predictive algorithms for heart failure decompensation.              | Number and rate of heart failure decompensation prediction (HFPred) risk scores successfully generated with complete data collection per person (rate defined as number of scores generated per week during the pilot)  | End of pilot              |

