| To validate the capability of the SHAPES Platform and Digital Solutions to gain the care professionals' trust and acceptance  | Exploration of healthcare practitioners' views on integration and alignment of the SHAPES platform and Digital Solutions with current care pathways   | After pilot  |
| To validate the capability of the SHAPES Platform and Digital Solutions to contribute for the reduction of the  | Change in health service utilisation for unscheduled care related to heart failure and diabetes as measured by: 
 
• Number of hospitalisations
 
• A&E attendances
 
 | 3 months prior to baseline and end of pilot
3 months prior to baseline and end of pilot |

|   |  |  |
|---|--|--|
| workload of medical professionals   | 
 
• Out of hours contacts
 
• Contacts with specialist services
 
   | 3 months prior to baseline and end of pilot
3 months prior to baseline and end of pilot |
| To validate the capability of the SHAPES Platform and Digital Solutions to deliver efficiency gains in health and care delivery across Europe | Economic impact of the intervention as measured by comparing the cost of the intervention (devices, SHAPES platform and digital solutions; staffing) versus the cost of unscheduled care related to heart failure and diabetes during the pilot. | After the pilot  |

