| Baseline Questionnaires ( Barthel Index; EHFS; Gijon Scale; MARS; BMQ; EQ-5D-5L; GSES; OSSS-3; HLM1; participation measure; WHOQOL-BREF ) Medical history data; Demographic data; Technical data; Laboratory results; Unscheduled care; Current prescribed medication   |                |                 | X              |                   |                            |   |                                   |                |
| During pilot ( collected via SHAPES app ) Blood pressure, heart rate, oxygen saturation, weight (daily); Blood glucose (as directed); Heart failure symptom survey (daily); MARS questionnaire (weekly); Unscheduled care updates (as they occur); Prescribed medication updates (weekly); SHAPES app tracking data (continuous); Adverse events; Contact with researchers. |                |                 |                | X                 |                            |   |                                   |                |
| End of pilot Questionnaires ( UEQ-S; SUS; MARS; BMQ; EQ-5D-5L; GSES; OSSS-3; HLM1; participation measure; WHOQOL-BREF; technology acceptance measure ); Demographic data.   |                |                 |                |                   | X                          |   |                                   |                |
| Participant interview  |                |                 |                |                   |                            | X   |                                   |                |
| 3-month follow-up Questionnaires ( EQ-5D-5L; GSES; OSSS-3; HLM1; participation measure; WHOQOL-BREF )   |                |                 |                |                   |                            | X   | X                                 |                |
| HSC Health and social care; EHFS European Heart Failure Self-Care Behaviour Scale; MARS Medication Adherence Report Scale; BMQ Beliefs about Medicines Questionnaire; GSES General Self-Efficacy Scale; OSSS-3 Oslo Social Support Scale-3; HLM1 Single-item Health Literacy Measure; WHOQOL-BREF Abbreviated World Health Organisation Quality of Life questionnaire                     |                |                 |                |                   |                            |   |                                   |                |

Figure 1: Service user participant timeline

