#### **3.8.3 Data collection tools**

Data collection for the service user will be documented on to a case report form (CRF). Paper questionnaires will form part of the CRF and the CRF will be the source for questionnaires. The source for all data points can be found in the data plan. The CRF will then be transcribed onto an online database using Microsoft Excel and analysed using Microsoft Excel and IBM SPSS Software this will be stored on NHSCT computers behind the NHSCT firewall. Specific data will be securely shared with other SHAPES partners and appropriate Data Processing Agreements will be in place.

Data collection for the interviews with healthcare professionals may be audio and visually recorded. This will be completed either by using videoconferencing software e.g., Zoom or using a Dictaphone. Interviews will be transcribed either manually or using software and the transcript validated by a second researcher.

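### The baseline look-back for A&E, out-of-hours and specialist contacts reads as one month, but the change outcomes built on them start three months before baseline

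*Protocol*

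**What the plan says.** Section 3.8.1 of the Protocol, under baseline procedures, lists the unscheduled care to be recorded as "hospitalisations (previous 3 months), and previous month hospital readmissions, A&E attendances, out of hours care, specialist service contacts, emergency ambulance call outs".

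The outcomes that use these items are defined in section 3.4:

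- **Secondary outcome.** The change is in hospitalisation rate and in "A&E attendance rate (attendance/month) three months prior to baseline compared with 3 months during the pilot". Table 1 gives the timepoints for both rates as "3 months prior to baseline and end of pilot".
- **Tertiary outcome.** Table 1 repeats the same timepoints separately for number of hospitalisations, A&E attendances, out-of-hours contacts and specialist contacts. No per-month scaling is stated for these.

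Two other places might have settled the look-back and do not. The baseline row of the timeline in section 3.5 reads "Medical history data; Demographic data; Technical data; Laboratory results; Unscheduled care; Current prescribed medication", with no window. Section 3.8.3 says "The source for all data points can be found in the data plan"; that plan is not among the documents at hand.

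For the pilot period, section 3.8.1 (study visits and procedures) has updates to the same items "recorded from medical notes".

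**The concern.** The baseline sentence contains two windows. The three-month one is in brackets directly after hospitalisations. The one-month one comes next and opens the list that holds everything else. Staff who follow the sentence as written would plausibly extract one month of A&E, out-of-hours and specialist contacts, while the outcome definitions require three.

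This goes beyond detail that a statistical analysis plan could supply later. It decides which data exist at baseline, and no analysis can recover months that were not extracted unless the notes are read again.

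One secondary outcome (A&E rate) and three tertiary items (A&E, out-of-hours and specialist contacts) are at stake. In Table 1, the A&E rate is one of only two measures mapped to the objective on better patient outcomes. Hospitalisations are consistent at three months. The primary outcome (app openings) does not use these data, and the correlation of the heart failure risk score with unscheduled care uses the pilot period only.

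**Working it through.** The Protocol gives no event rate, power calculation or target precision, so it has no figure to reproduce. The check compares the windows and then sizes the consequence.

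**Windows side by side**

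| Item | Look-back in section 3.8.1 | Look-back in the outcome definition (section 3.4) |
|---|---|---|
| Hospitalisations | 3 months | 3 months |
| A&E attendances | 1 month, or none stated | 3 months (secondary and tertiary) |
| Out-of-hours contacts | 1 month, or none stated | 3 months (tertiary) |
| Specialist contacts | 1 month, or none stated | 3 months (tertiary) |

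Neither reading of section 3.8.1 gives three months for the last three rows. The figures below apply to the one-month reading.

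**Inputs.** Target of 30 service users (section 3.6). Pilot length: "Participants will be asked to use the app and connected devices for 12 weeks" (section 3.3), or 3 months as in the secondary outcome. One month is taken as 365.25/12 = 30.4375 days. Rates of 0.05, 0.1 and 0.2 events per person per month are assumptions.

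**Days not collected.** 3 × 30.4375 = 91.3 days needed and 30.4 collected, so 60.9 are missing (67%).

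**Precision of the change in monthly rate.** With a constant event rate *r*, pre-pilot window *t* months and pilot length *p* months, the standard error (SE) is sqrt(*r*(1/*t* + 1/*p*)/30).

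- 12-week pilot: *p* = 84/30.4375 = 2.760. SE ratio, one month to three months = sqrt(1 + 1/2.760) / sqrt(1/3 + 1/2.760) = 1.167/0.834 = 1.40.
- 3-month pilot: sqrt(4/3) / sqrt(2/3) = 1.41.

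The rate cancels in this ratio. Differences between people also leave it unchanged, because a constant personal rate drops out of the paired difference. A simulation of 200,000 people, Poisson and gamma-Poisson with shape 0.5, gave ratios of 1.394 to 1.405 and a mean change within 0.002 of zero.

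**Absolute size**, with *p* = 2.760. Half-width = 1.96 × SE. Expected participants with any pre-pilot event = 30 × (1 − exp(−*r* *t*)).

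| Assumed rate | Half-width, 1 month | Half-width, 3 months | With any event, 1 month | With any event, 3 months |
|---|---|---|---|---|
| 0.05 | 0.093 | 0.067 | 1.5 | 4.2 |
| 0.1 | 0.132 | 0.094 | 2.9 | 7.8 |
| 0.2 | 0.187 | 0.133 | 5.4 | 13.5 |

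For example, at 0.1: 1.96 × sqrt(0.1 × 1.3623/30) = 0.132, and 1.96 × sqrt(0.1 × 0.6957/30) = 0.094.

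**Tertiary counts.** If a one-month count were set against a pilot-period count with no allowance for exposure, no true change would look like a rise of 2.760/1 = 2.76-fold (12 weeks) or 3/1 = 3.0-fold (3 months). The Protocol does not prescribe that comparison.

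**The case against.** The strongest reply is grammatical. The one-month phrase may belong to readmissions alone. Section 3.8.1 is then silent on the other items, and Table 1 shows item by item that three months are needed. This stands as far as it goes: on that reading the sentence is incomplete and does not contradict the outcomes. It still does not tell the person filling in the form how far back to look, and it is the less natural reading, because a second window is introduced straight after hospitalisations.

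A second reply is that no data loss is shown. Pilot-period updates come from medical notes, notes can be read back to any date, and the data plan may already say three months. This also stands. In that case only the wording needs correcting.

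A third is that little is lost. The A&E outcome is a monthly rate, unbiased under a constant rate, and forms half of one of 16 secondary outcomes in a single-arm pilot whose size was chosen pragmatically. Even with three months, the half-width is 134%, 94% and 67% of the assumed rates of 0.05, 0.1 and 0.2; with one month it is 186%, 132% and 94%. At the lowest rate the normal approximation is poor, with about 1.5 expected baseline events. These points limit the weight of the finding. They do not remove the mismatch: the outcome as defined cannot be computed from one month of data.

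The apparent rise in raw counts is a warning about a possible misuse, and the conclusion does not rest on it.

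**Conclusion.** The concern holds. On its natural reading, section 3.8.1 collects about one third of the pre-pilot period that section 3.4 and Table 1 require for one secondary outcome and three tertiary items. The cost is precision and fidelity to the definition: a standard error 1.40 to 1.41 times as large for the change in A&E rate, and an estimate that covers a different period from the one defined.

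The ratio assumes a constant event rate within each person; the absolute figures also depend on the assumed rates. Absence of bias rests on the same constancy. Section 3.7 allows recruitment from in-patient lists, so attendances could cluster shortly before enrolment, and one-month and three-month windows would then measure different things. The documents give nothing to size that.

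Confidence is medium, because the sentence can be read another way and the data plan is not at hand. If three months are in fact collected, none of these losses arises. The point should be fixed, but it does not threaten the pilot's primary aim.

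**What to change.** In the baseline procedures of section 3.8.1, the case report form and the data plan, state the look-back for A&E attendances, out-of-hours care and specialist contacts as the three months before baseline. Record event dates, from medical notes where possible. If baselines have already been taken with one month, re-read the notes for the two earlier months.

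The cost is one line in each document and slightly more record extraction for up to 30 participants.

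Two smaller points can be settled in the same edit, though the finding does not depend on them:

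- State that the tertiary change items are expressed per month of exposure, as the secondary rates already are.
- Make the secondary outcome agree with itself. Table 1 describes it as "Change in use of unscheduled care related to heart failure and diabetes as measured by", while the secondary outcome list carries no such restriction by condition.
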